9.3 POPULATIONS FOR ANALYSES

For purposes of analysis, the following populations are defined ([Table 5](#)):

Table 5 - Populations for analyses

| Population | Description |
|------------|---|
| Screened | All participants who sign the ICF. |
| Randomized | All screened participants who have a treatment kit number allocated and recorded in the IRT database, regardless of whether the treatment kit was used or not. |
| ITT | All participants randomized irrespective of rescue therapy use and compliance with the study protocol and procedures. Participants will be analyzed in the treatment group to which they are randomly assigned. |
| Safety | All participants randomly assigned to IMP and who take at least 1 dose of IMP. Participants will be analyzed according to the treatment they actually received. |
| ADA | All participants from the safety population with at least 1 postbaseline valid ADA sample after drug administration. |
| PK | All participants from the safety population with at least 1 valid PK sample available for analysis. |

ADA: antidrug antibody, ICF: informed consent form, IRT: interactive response technology, ITT: intent to treat, PK: pharmacokinetic.

9.4 STATISTICAL ANALYSES

The statistical analysis plan will be developed and finalized before database lock and will describe the participant populations to be included in the analyses and procedures for accounting for missing, unused, and spurious data. This section is a summary of the planned statistical analyses of the primary and secondary endpoints.

9.4.1 Efficacy analyses

Table 6 - Efficacy analyses

| Endpoint | Statistical Analysis Methods |
|----------|---|
| Primary | Primary analysis: The primary efficacy endpoint will be analyzed in all participants randomized, using all HbA1c values measured at baseline and Week 30 (observed or imputed), regardless of treatment discontinuation or initiation of rescue therapy. The primary analysis method for the primary efficacy endpoint will be an ANCOVA model with missing values imputed by MI analysis method in 2 parts as follows: 
1. Missing endpoint data in participants who prematurely discontinue the IMP before the Week 30 visit will be imputed using a model estimated from participants in the same treatment arm who prematurely discontinue the IMP before the Week 30 visit but have the measurement for the endpoint (retrieved dropouts). Considering that the number of participants in each treatment arm who discontinue the IMP but have the measurement for the endpoint is expected to be small, a simple imputation model will be used, where only the baseline measurements are included as the predictor. Each treatment group will have their own imputation model. Missing data will be imputed using the regression method. |

| Endpoint | Statistical Analysis Methods |
|----------|---|
| | 
2. Missing endpoint data in all participants, including those in the efpeglenatide arms, who stay on the IMP until the Week 30 visit, will be imputed separately, using a model estimated from participants in the placebo group who stay on the IMP until the Week 30 visit and have the endpoint data available. The imputation model will include the randomization strata and corresponding baseline values without including any intermediate. Missing data will be imputed using the regression method.
 
In this analysis, missing endpoint values will be imputed 10 000 times to generate 10 000 data sets with complete data. Each of the completed datasets after the imputation will be analyzed by the ANCOVA model with treatment groups, randomization strata, and geographical regions as fixed effects and the corresponding baseline HbA1c values as a covariate.
 
The baseline value is defined as the last available value prior to the first dose administration of IMP or the last available value on or before the date of randomization if not treated with the double-blinded IMP.
 
The results from the 10 000 analyses will be combined using Rubin's formula and provide the adjusted mean change in HbA1c from baseline to Week 30 (regardless of treatment discontinuation or initiation of rescue therapy) for each treatment group, as well as the difference between each efpeglenatide dose and placebo and the 95% CI for the difference.
 
A hierarchical procedure will be applied to adjust for the multiplicity of comparison on the primary endpoint as follows:
 
• First, the highest dose of efpeglenatide (6 mg) will be compared to placebo to demonstrate superiority of this dose versus placebo.• If superiority is demonstrated for efpeglenatide 6 mg, the superiority of 4 mg dose of efpeglenatide versus placebo will be tested.• If superiority is also demonstrated for 4 mg dose, the lowest dose (2 mg) will be tested for superiority over placebo. 
When the superiority is not obtained in a step, the sequential testing procedure will be stopped.
 
As noted, the number of retrieved dropouts is expected to be small, and there may not be sufficient data to support the imputation approach in item 1 described above. If there are fewer than 5 participants in any treatment arms who prematurely discontinue the IMP before the Week 30 visit but have the HbA1c measurements for the endpoint, a back-up imputation method for the primary efficacy analysis will be used. In particular, missing endpoint data in all participants in both efpeglenatide and placebo groups, regardless of staying on the IMP or not, will be imputed using a model estimated from participants in the placebo group with endpoint data, where randomization strata and corresponding baseline values are included as the predictors. Missing data will be imputed using the regression method.
 
Summary statistics (for screening value, baseline value, observed values, and observed changes from baseline) at scheduled visits will be provided by treatment group for HbA1c value over the whole treatment period including the 26-week Treatment Extension Period. The summary will include the number of observations, mean, SD, SE, minimum, median, and maximum. Graphical presentations will also be used to examine trends over time using mean values (\pmSE) and mean changes from baseline (\pmSE) at each of the scheduled visits (using OCs).
 
Sensitivity analysis:
 
Tipping-point analysis based on the same MI method as described above will be performed to examine the robustness of the results from the primary analysis. A penalty δ will be added to participants in efpeglenatide groups (2, 4, or 6 mg) who have no HbA1c data at Week 30. The penalty will be gradually increased to evaluate at which level the conclusion of the analyses in terms of statistical significance is changed for each efpeglenatide dose group. The tipping point is the penalty level, at which the magnitude of efficacy reduction in participants
 |

| Endpoint | Statistical Analysis Methods |
|----------|---|
| | 
without HbA1c data at Week 30 creates a shift in the treatment effect of efpeglenatide from being statistically significantly better than placebo to a nonstatistically significant effect. Least squares mean difference between each efpeglenatide dose and placebo and its associated p-value will be provided for each penalty level.
 
The primary endpoint will be assessed too by an ANCOVA model with missing values imputed by control-based MI method (copy to reference) under the MNAR framework in the ITT population. Data will be imputed 10 000 times:
 
• For participants in the placebo group, missing data will be imputed based on the placebo group data.• For participants in the efpeglenatide groups, missing data will be imputed as if the participants were on placebo throughout the study. 
In particular, a 2-step approach will be used as follows:
 
• Step 1: Use the Markov Chain Monte Carlo method conjunction with the IMPUTE=MONOTONE option in PROC MI to create an imputed data set with a monotone missing pattern.• Step 2: Based on the MONOTONE data sets obtained from Step 1, build the imputation model using the regression method on data from the placebo group, and use the built model conditional on participant's previous observed data to impute the missing data in both placebo and efpeglenatide groups. The imputation model will include the randomization stratum of HbA1c value at screening (<8%, ≥8%), and the randomization stratum of SU use (Yes, No). This will be implemented using MNAR statement in PROC MI. 
Each of the complete datasets after the imputation will be analyzed using the same ANCOVA model as used for the primary analysis. Results from each complete dataset will be combined using Rubin's formula.
 
Descriptive analyses will be conducted to explore missing data patterns for HbA1c in the primary efficacy analysis, with number and percentage of participants in each of the following categories presented by treatment group.
 
• Pattern 1: participants without baseline values, if any.• Pattern 2: participants with baseline values but without postbaseline values during the 30-week Core Treatment Period.• Pattern 3: participants with baseline values and at least 1 postbaseline value during the 30-week Core Treatment Period but not at Week 30.• Pattern 4: participants with baseline values and a Week 30 value during the 30-week Core Treatment Period. 
HbA1c values by visit will be presented by missing data pattern for each treatment group, using descriptive statistics and/or graphs
 
Assessment of treatment effect by subgroup:
 
The primary efficacy endpoint will be further analyzed to examine the consistency of the treatment effect across the subgroups defined by the following baseline covariates:
 
• Race (white, black or African American, Asian, Other) (any race groups with fewer than 5 participants may be combined with "Other" category as appropriate).• Ethnicity (Hispanic, Not Hispanic).• Age group (<50, ≥50 to <65, ≥65 to <75, ≥75 years) (any category with fewer than 5 participants may be combined with another category as appropriate).• Gender (Male, Female).• Baseline HbA1c (<8.0%, ≥8.0%). |

| Endpoint | Statistical Analysis Methods |
|---|---|
| | 
 Baseline BMI (<30 kg/m², ≥30 kg/m²). Diabetes duration (<10 years, ≥10 years). Country. United States/non-United States. Antidiabetic drugs at the time of screening (Lantus, Lantus + OAD). SU use at screening (Yes, No). 
The treatment effects (efpeglenatide 2, 4, or 6 mg versus placebo) across the subgroups defined for each of these factors will be estimated for the change from baseline to Week 30 in HbA1c in the ITT population and using a similar approach as applied to the analysis for the primary efficacy endpoint. The ANCOVA model will include treatment groups (efpeglenatide 2, 4, or 6 mg, placebo) and randomization stratum of screening HbA1c (<8%, ≥8%), randomization stratum of SU use (Yes, No), subgroup factor, treatment-by-subgroup factor, and region as fixed factors and using the baseline HbA1c value as a covariate. The adjusted estimates of treatment mean differences (each efpeglenatide dose versus placebo) with SE and 95% CIs will be provided across the subgroups, as appropriate. A graphical presentation of the results (ie, forest plot) will also be provided.
 
In the case that the subgroup factor is identical or similar to a randomization strata factor (eg, baseline HbA1c, SU use), only the subgroup factor (as a single factor or an interaction term) will be included in the model in order to avoid the issue of collinearity in the analysis. The corresponding strata factor will not be included in the model. In case that the subgroup factor is country, the region will not be included in the model.
 |
| Secondary | |
| Change from baseline to Week 56 in HbA1c | Continuous secondary efficacy endpoints will be analyzed using the same ANCOVA model with missing values imputed by MI method as the method used for the primary efficacy endpoint analysis. Differences between treatment groups and CIs will be estimated by this method. |
| Change from baseline to Week 30 in FPG | Categorical efficacy endpoints will be analyzed by the Cochran Mantel-Haenszel method stratified by the randomization strata. For the HbA1c <7.0% analysis, participants with missing HbA1c data at Week 30 or Week 56 will be considered nonresponders in the ITT population. |
| Change from baseline to Weeks 30 and 56 in body weight | Summary statistics (for screening value, baseline value, observed values, and observed changes from baseline) at scheduled visits will be provided for each treatment group over the whole treatment period including the 26-week Treatment Extension Period. The summary will include the number of observations, mean, SD, SE, minimum, median, and maximum. |
| Number of participants with HbA1c <7.0% at Week 30 (yes/no) | Graphical presentations will also be used to examine trends over time using mean values (±SE) and mean changes from baseline (±SE) at each of the scheduled visits (using OCs). |
| Multiplicity considerations | 
To control the family-wise Type I error, a step-down testing procedure will be applied. For the primary efficacy endpoint (change from baseline to Week 30 in HbA1c), the 3 efpeglenatide doses will be tested in the order of 6 mg, 4 mg, and 2 mg. once the primary endpoint is statistically significant at $\alpha = 0.05$ (2-sided) for all 3 efpeglenatide doses, a hierarchical testing procedure will be performed to test the following study secondary efficacy endpoints by the following prioritized order:
 
 1. HbA1c <7% at Week 30 for efpeglenatide 6 mg versus placebo (yes/no). 2. Change from baseline to Week 30 in body weight (kg) for efpeglenatide 6 mg versus placebo. 3. HbA1c <7% at Week 30 for efpeglenatide 4 mg versus placebo (yes/no). 4. Change from baseline to Week 30 in body weight (kg) for efpeglenatide 4 mg versus placebo. 5. HbA1c <7% at Week 30 for efpeglenatide 2 mg versus placebo (yes/no). |

| Endpoint | Statistical Analysis Methods |
|--|--|
| | 
6. Change from baseline to Week 30 in FPG (mmol/L, mg/dL) for efpeglenatide 6 mg versus placebo.7. Change from baseline to Week 30 in FPG (mmol/L, mg/dL) for efpeglenatide 4 mg versus placebo.8. Change from baseline to Week 56 in body weight (kg) for efpeglenatide 6 mg versus placebo.9. Change from baseline to Week 56 in body weight (kg) for efpeglenatide 4 mg versus placebo.10. Change from baseline to Week 56 in HbA1c (%) for efpeglenatide 6 mg versus placebo.11. Change from baseline to Week 56 in HbA1c (%) for efpeglenatide 4 mg versus placebo.12. Change from baseline to Week 56 in HbA1c (%) for efpeglenatide 2 mg versus placebo.13. Change from baseline to Week 56 in body weight (kg) for efpeglenatide 2 mg versus placebo.14. Change from baseline to Week 30 in body weight (kg) for efpeglenatide 2 mg versus placebo. |
| Exploratory endpoints See Section 3 | 
The testing will stop as soon as an endpoint for an efpeglenatide dose is found to be not statistically significant at $\alpha = 0.05$ (2-sided) for 1 efpeglenatide dose. No multiplicity adjustment will be made on other secondary efficacy variables or the comparison of other efpeglenatide dose versus placebo than mentioned above.
 
Comparisons of time-to-event endpoints between treatment groups will be performed using the Cox proportional hazards regression model with the treatment groups (efpeglenatide 2, 4, or 6 mg, placebo), randomization stratum of screening HbA1c ($<8\%$, $\geq 8\%$), randomization stratum of SU use (yes/no) and geographical region as the factors. The curve of the cumulative incidence of participants with rescue therapy initiation will be estimated using Kaplan-Meier method by treatment group.
 
Summary statistics (for screening value, baseline value, observed values, and observed changes from baseline) at scheduled visits will be provided for each treatment group over the whole treatment period including the 26-week Treatment Extension Period. The summary will include the number of observations, mean, SD, SE, minimum, median, and maximum. Graphical presentations will also be used to examine trends over time using mean values ($\pm SE$) and mean changes from baseline ($\pm SE$) at each of the scheduled visits (using OCs).
 |

ANCOVA: analysis of covariance, BMI: body mass index, CI: confidence interval, FPG: fasting plasma glucose, HbA1c: hemoglobin A1c, ITT: intent to treat, MI: multiple imputation, MNAR: missing not at random, OC: observed cases, SD: standard deviation, SE: standard error, SMPG: self-monitored plasma glucose, SU: sulfonylurea.

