2. Missing endpoint data in all participants, including those in the efpeglenatide arms, who stay on the IMP until the Week 30 visit, will be imputed separately, using a model estimated from participants in the placebo group who stay on the IMP until the endpoint visit and have the Week 30 data available. The imputation model will include the randomization strata and corresponding baseline values but without including any intermediate values. Missing data will be imputed using the regression method.

In this analysis, missing endpoint values will be imputed 10 000 times to generate 10 000 data sets with complete data. Each of the completed datasets after the imputation will be analyzed by the ANCOVA model with the treatment groups (efpeglenatide 2, 4, or 6 mg, or placebo), randomization stratum of screening HbA1c (<8%, ≥8%), randomization stratum of SU (yes/no) and geographical region as fixed effects, and baseline HbA1c value as a covariate. The baseline

value is defined as the last available value prior to the first dose administration of IMP or the last available value on or before the date of randomization if not treated with the double-blinded IMP.

The results from the 10 000 analyses will be combined using Rubin's formula to provide the adjusted mean change in HbA1c from baseline to Week 30 (regardless of treatment discontinuation or initiation of rescue therapy) for each treatment group, as well as the difference between each efpeglenatide dose and placebo and the 95% confidence interval (CI) for the difference.

As noted, the number of retrieved dropouts is expected to be small, and there may not be sufficient data to support the imputation approach in item 1 described above. If there are fewer than 5 participants in any treatment arms who prematurely discontinue the IMP before the Week 30 visit but have the HbA1c measurements for the endpoint, a back-up imputation method for the primary efficacy analysis will be used. In particular, missing endpoint data in all participants in both efpeglenatide and placebo groups, regardless of staying on the IMP or not, will be imputed using a model estimated from participants in the placebo group with endpoint data, where randomization strata and baseline HbA1c value are included as the predictors. Missing data will be imputed using the regression method.

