5.1 INCLUSION CRITERIA

Participants are eligible to be included in the study only if all of the following criteria apply:

Age

I 01. Participant must be ≥ 18 years of age at the time of signing the informed consent.

Type of participant and disease characteristics

I 02. Participants with T2DM.

I 03. Diabetes diagnosed at least 1 year before screening.

I 04. Participants on a background antidiabetic treatment for which all of the below apply:

- a) Participants on basal insulin regimen alone or in combination with OAD(s) for at least 6 months prior to screening,
- b) Participants on insulin glargine 100 U/mL as only basal insulin for at least 3 months prior to screening,
- c) Participants on stable daily dose of insulin glargine 100 U/mL ($\pm 20\%$ total dose) for at least 2 months prior to screening.

I 05. HbA1c between 7.0% and 10.0% (inclusive) measured by the central laboratory at screening.

Informed consent

I 06. Capable of giving signed informed consent as described in Appendix 1 ([Section 10.1.2](#)) which includes compliance with the requirements and restrictions listed in the informed consent form (ICF) and in this protocol.

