- Dose regimen: Administered as per Investigator prescription and in accordance with local labeling. If metformin is taken as the only OAD in addition to the basal insulin, it should be at a dose of ≥1500 mg/day (or maximum tolerated dose or as per country regulation if less). Dose(s) of background OAD(s) should be kept stable throughout the study unless dose reduction is needed for safety reasons.

6.1.2.2 **Rescue therapy**

Rescue medication(s) that will be used to treat unacceptable hyperglycemia if a participant's glycemia reaches an applicable rescue threshold, is considered NIMP for this study. The threshold values are defined in [Table 4](#) and are dependent on study period.

Table 4 - Rescue criteria

| Time in study | Threshold |
|---|--|
| From randomization up through the scheduled Week 8 visit (Visit 5). | FPG >15.0 mmol/L (>270 mg/dL) |
| After the Week 8 visit up through the scheduled Week 12 visit (Visit 6). | FPG >13.3 mmol/L (>240 mg/dL) |
| After the Week 12 visit (Visit 6) through the end of the 30-week Core Treatment Period. | FPG >11.1 mmol/L (>200 mg/dL) or HbA1c ≥8.5% |
| After the Week 30 Visit (Visit 9) through the end of the Treatment Extension Period. | FPG >8.9 mmol/L (>160 mg/dL) or HbA1c ≥8.0% |

FPG: fasting plasma glucose, HbA1c: hemoglobin A1c

Routine fasting SMPG and central laboratory alerts on FPG (and HbA1c from Week 12 [Visit 6] onwards) will be set up to ensure that glycemic parameter results remain below the predefined thresholds.

If a fasting SMPG value exceeds the specific glycemic limit on 1 day, the participant must check it again during the following 2 days. If all the SMPG values in 3 consecutive days exceed the specific limit, the participant should contact the Investigator and a central laboratory FPG measurement (and HbA1c from Week 12 onwards) be performed as soon as possible for confirmation.

Upon receipt of a central laboratory alert for either FPG or HbA1c, a central laboratory retest must be completed and confirmed as exceeding the threshold for rescue before rescue therapy is initiated. The retest confirmation should be performed as soon as possible during an unscheduled visit.

In the event that a confirmatory FPG and/or HbA1c value exceeds the threshold, the Investigator should ensure that no reasonable explanation exists for insufficient glucose control and in particular that:

- The increased FPG has been tested at a fasting status (ie, no food or liquid intake [except water] for ≥ 8 hours).

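### The Cox model for time to rescue carries HbA1c only as a <8%/≥8% stratum; adding continuous baseline HbA1c would recover a little power (about 0 to 6 points under assumed inputs)

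*Protocol*

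**What the plan says.** Protocol 9.4.1, Table 6, under exploratory endpoints: "Comparisons of time-to-event endpoints between treatment groups will be performed using the Cox proportional hazards regression model with the treatment groups", followed by the screening HbA1c stratum (<8%, ≥8%) and ending with "randomization stratum of SU use (yes/no) and geographical region as the factors". The synopsis gives the same list. The only time-to-event efficacy endpoint in Protocol Section 3, Table 1 is time to initiation of rescue therapy, which is tertiary/exploratory.

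The primary ANCOVA carries the same strata and one more term. The synopsis has "geographical region as fixed effects, and baseline HbA1c value as a covariate"; Table 6 has "randomization strata, and geographical regions as fixed effects and the corresponding baseline HbA1c values as a covariate".

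The rescue limits in Protocol 6.1.2.2, Table 4 are absolute:
- To Week 8 and then to Week 12, they are FPG limits only (15.0, then 13.3 mmol/L).
- After Week 12 through Week 30: "FPG >11.1 mmol/L (>200 mg/dL) or HbA1c ≥8.5" (in %).
- After Week 30: "FPG >8.9 mmol/L (>160 mg/dL) or HbA1c ≥8.0" (in %).

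Crossing a limit does not start rescue by itself. Section 6.1.2.2 requires a central laboratory retest and a check for other explanations, after which rescue is permitted rather than mandated. The entry criterion is "HbA1c between 7.0% and 10.0% (inclusive) measured by the central laboratory at screening".

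SAP 2.1.3.3 still lists time to rescue. However, SAP 1.6 states that the planned efficacy evaluations were not performed after early termination, and SAP 2.4 and 2.4.3 provide only descriptive summaries of HbA1c, FPG, body weight and the HbA1c 7% responder proportion. No Cox model appears in the SAP.

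**The concern.** The protocol's own rescue rule links starting HbA1c to this endpoint, and a two-level stratum captures only part of that link. In the ≥8% stratum, a participant entering at 8.1% is already under the 8.5% limit, while one at 10.0% must fall by more than 10.0 − 8.5 = 1.5 points to be under it. In the <8% stratum, room below the 8.0% extension limit is 8.0 − 7.0 = 1.0 point at one end and 8.0 − 7.9 = 0.1 at the other. The planned model treats the members of each pair alike.

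If baseline HbA1c predicts rescue within strata, leaving it out of a Cox model attenuates the log hazard ratio and lowers power for each dose-versus-placebo comparison. The value is already collected and already in the ANCOVA, and no reason is given for dropping it here.

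**Working it through.** **1. The plan's own power figure.** Protocol 9.2: n = 100 per arm, SD 1.1, two-sided alpha 0.05.
- SE of the difference = 1.1 × √(2/100) = 0.1556.
- At −0.5: 0.5/0.1556 − 1.96 = 1.25, power 89.5% (89.2% by noncentral t); stated 89%.
- At −0.6: 0.6/0.1556 − 1.96 = 1.90, power 97.1% (97.0%); stated 96%.

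These agree closely, but they concern HbA1c change. The documents give no power, event rate or hazard ratio for time to rescue, so its size must be simulated.

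**2. Simulation.** Four arms of 100, 6 mg versus placebo. Each simulated trial is fitted twice:
- planned form: treatment + HbA1c stratum;
- extended form: the same + continuous baseline HbA1c.

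The SU stratum and region were left out of both and given no effect. There were 1,000 to 1,500 trials per effect scenario and 2,000 under the null.

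Assumptions not in the documents: screening HbA1c normal (8.2, SD 0.7) truncated to 7–10; baseline = screening + noise of SD 0.25; about 12% dropout.

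*(A) Proportional hazards*, true treatment HR 0.5, 12–32% with an event:

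| HR per 1% HbA1c | Events | log HR, planned → extended | SE | Power |
|---|---|---|---|---|
| 1.0 | 12% | −0.731 → −0.732 | 0.407 → 0.408 | 43.3% → 43.1% |
| 1.5 | 28% | −0.693 → −0.701 | 0.259 → 0.259 | 78.7% → 78.7% |
| 2 | 30% | −0.687 → −0.707 | 0.253 → 0.254 | 80.5% → 81.9% |
| 3 | 16% | −0.670 → −0.698 | 0.353 → 0.354 | 47.1% → 50.3% |
| 3 | 32% | −0.646 → −0.700 | 0.244 → 0.245 | 76.7% → 82.3% |

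*(B) Threshold model*: HbA1c ≥8.5% at Weeks 12 and 30, ≥8.0% at Weeks 43 and 56 (the post-baseline HbA1c visits in SAP Appendix B). Assumed placebo change −0.5; FPG not modelled. Treatment effect 0.5 in the rows shown:

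| Slope on baseline | Residual SD | Rescued at limit | log HR, planned → extended | Power |
|---|---|---|---|---|
| 0.4 | 0.9 | all | −0.701 → −0.718 | 87.8% → 88.0% |
| 0.6 | 0.9 | half | −0.672 → −0.691 | 70.6% → 71.2% |
| 0.6 | 0.9 | all | −0.665 → −0.694 | 81.9% → 84.8% |
| 0.8 | 0.9 | all | −0.641 → −0.683 | 80.4% → 84.2% |
| 0.6 | 1.1 | half | −0.545 → −0.553 | 58.1% → 59.7% |

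Model B applies the 8.5% limit at the Week 12 visit itself, where Table 4 still has an FPG limit only. If anything, this favours baseline HbA1c.

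**3. Where the power goes.** The extended/planned SE ratio is 1.002 to 1.006 in every scenario, so the standard error never falls. The change is in the estimate: in the last row of A, 1 − 0.646/0.700 = 7.7% attenuation. Relative efficiency of the planned model there is (0.646/0.244)² / (0.700/0.245)² = 7.01/8.16 = 0.86; across the effect scenarios it is about 0.86 to 1.00.

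**4. Validity.** Under the null, rejection is 4.7–5.9% without and 5.1–5.7% with the covariate. Monte Carlo SE is √(0.05 × 0.95/2000) = 0.5 points, so both are compatible with 5%.

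**5. Cross-check with other inputs.** A separate threshold run used the same visits, an SD of HbA1c change near the protocol's 1.1, assumed mean HbA1c 8.4 and placebo change −0.3 (800 trials each):
- slope 0.6, effect −0.5: 77.4% → 78.1%;
- slope 0.8, effect −0.5: 71.0% → 73.4%;
- slope 0.9, effect −0.5: 70.5% → 73.6%;
- slope 0.8, effect −0.6: 85.4% → 87.0%;
- slope 0.8, effect −0.5, half of crossings rescued: 60.4% → 60.1%.

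These gains are about 0 to 3 points, inside the range above.

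**The case against.** The strongest reply is that the plan is already sound. Adjusting for the stratification factors is a standard choice, randomization protects the test, and the stratum carries part of the baseline information. Lantus titration after Week 8 in all arms, FPG-only limits through Week 12, the retest and investigator judgement all loosen the tie between entry HbA1c and rescue. The endpoint is exploratory, outside the testing hierarchy, and has no power target. All of this stands, and it is why the gain is small and the point optional. Collinearity is no reason to leave the covariate out, since the ANCOVA already carries stratum and baseline together.

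Four stronger readings are tempting, and the documents do not support them:
- *Precision is lost.* In a Cox model the covariate does not reduce the standard error of the log hazard ratio; here it rises by 0.2–0.6%.
- *The planned hazard ratio is biased.* The shift toward 1 is largely the difference between a less and a more conditional hazard ratio (non-collapsibility), and type I error is preserved.
- *The loss is as much as 8 points.* A simulation can show gains of about 3 to 8 points if it tests HbA1c at Weeks 18 and 24, uses person-level SDs of 0.6–0.8 and an effect of −0.30 to −0.35, and treats every crossing as rescue. But neither week is an HbA1c visit in SAP Appendix B (Week 18 is a telephone contact), Protocol 9.2 uses SD 1.1 and effects of −0.5 and −0.6, and Section 6.1.2.2 does not make rescue automatic.
- *A reported result is affected.* The SAP lists the endpoint but runs no Cox analysis.

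**Conclusion.** The point holds as an optional efficiency improvement to the protocol text, not as an error. The Cox model omits a continuous covariate that the rescue rule itself makes relevant and that the ANCOVA uses. The cost is an attenuated log hazard ratio and about 0 to 6 points of power. The threshold model gave 0 to 4; only the strongest assumed association (hazard ratio 3 per 1% HbA1c) approached 6; and with little association within strata the loss is nil. The direction follows from the model. The size depends on assumed HbA1c distribution, slope, residual SD, rescue fraction and dropout. Because the analysis is not run under the post-termination SAP, the practical weight is low.

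**What to change.** In Table 6 and the synopsis, add continuous baseline HbA1c as a covariate to the Cox model for time to initiation of rescue therapy, mirroring the ANCOVA term in "geographical region as fixed effects, and baseline HbA1c value as a covariate". Keep both randomization strata and region. State beside it that the hazard ratio is conditional on baseline HbA1c, as it already is on the strata and region.

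The cost is one phrase in two places and one degree of freedom. The baseline value is already scheduled for all participants and defined in the protocol, so no new data are needed. The SAP needs no change unless the Cox analysis is reinstated.
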